#### 6.1.1 Dosing regimen

Ribociclib will be dosed on a flat scale of 600 mg (e.g., 3 x 200 mg capsules) once daily for 3 weeks on/1 week off. A complete treatment cycle is defined as 28 days (refer to [Table 6-1](#)).

The patient must continue to meet all eligibility criteria on C1D1, as they did during the screening period. Refer to [Section 7.1](#) for more details

**Table 6-1 Dose and treatment schedule**

Study treatments	Pharmaceutical form and route of administration	Dose	Frequency and/or Regimen
Ribociclib	Capsule for oral use	600 mg/day	Daily (3 weeks on/1 week off)

### 6.1.1.1 Ribociclib administration

The following general guidelines should be followed for administration.

- Patients should be instructed to take their daily dose with a large glass of water (~250 ml) and swallow the required number of capsules at approximately the same time on each day. The capsules should be consumed over as short a time as possible (e.g. 1 capsule every 2 minutes) and can be taken without regard to meals. However, dietary habits around the time of dosing should be as consistent as possible throughout the study.
- At each visit, responsible site personnel will ensure that the appropriate dose of each study drug is administered and will provide the patient with the correct amount of study drug(s) for subsequent dosing. Patients will be instructed to return unused study drugs to the site at the end of each cycle.
- Patients should be instructed to swallow the capsules whole and not to chew or crush them.
- Any doses that are missed should be skipped and should not be replaced or made up during the next scheduled dosing or on a subsequent day, whichever applies.
- Patients must avoid consumption of grapefruit, pomelos, pomegranates, star fruits, Seville oranges or products containing the juice of each during the entire study and preferably 7 days before the first dose of study medications, due to potential CYP3A4/5 interaction with the study medications. Orange juice is allowed.
- If vomiting occurs during the course of treatment, no re-dosing of the patient is allowed before the next scheduled dose. The occurrence and frequency of any vomiting and/or diarrhea (or increased stool frequency) must be noted in the AEs section of the eCRF.
- If patient forgets to take his/her daily dose of ribociclib within 6 hours of the usual dosing time, then that day's dose should be omitted and the patient should continue treatment with the next scheduled dose
- The investigator (or his/her designee) must instruct the patient to take ribociclib exactly as prescribed. The patient should be instructed to contact the investigator (or his/her designee) if he/she is unable for any reason to take ribociclib as prescribed. All dosages prescribed and dispensed to the patient, and all dose changes during the study, must be recorded on the Dosage Administration Record eCRF. Patients must be advised to bring their unused ribociclib capsules/tablets to the investigative site at each visit.

### **6.1.2 Guidelines for continuation of treatment**

Patients will be treated until disease progression (as assessed by investigator per RECIST 1.1 or appropriate hematologic response criteria) or unacceptable toxicity death or discontinuation from study treatment for any other reason (e.g., withdrawal of consent, start of a new anti-neoplastic therapy or at the discretion of the investigator). Guidance for continuation of study treatment in case of toxicity (e.g. dose delay and/or modification) is provided in [Section 6.3](#).

### **6.1.3 Treatment duration**

Patients may continue treatment with the study drug until the patient experiences unacceptable toxicity that precludes further treatment, disease progression as assessed by the investigator (per RECIST 1.1 or appropriate hematological response assessment criteria), death and/or treatment is discontinued due to any other reason. The reason for end of treatment (EOT) will be recorded in the corresponding eCRF.

## **6.2 Dose escalation guidelines**

Not applicable.

## **6.3 Dose modifications**

### **6.3.1 Dose modification and dose delay**

For patients who do not tolerate the protocol-specified dosing schedule, dose adjustments are permitted in order to allow the patient to continue the study treatment. Any changes in LEE011 administration must be recorded on the Dosage Administration Record eCRF.

Ribociclib dose modification guidelines are described in [Section 6.3.2](#). Any planned variance from these guidelines in the view of the patient safety must be previously discussed with the sponsor unless there is an urgent need for action.

All dose modifications, interruptions or discontinuations must be based on the worst preceding toxicity as graded by the NCI Clinical Toxicity Criteria for adverse events (NCI-CTCAE version 4.03). Once a dose has been reduced during a treatment cycle, re-escalation will not be permitted during any subsequent cycle.

If the administration of ribociclib is interrupted for reasons other than toxicity, then treatment with the study drug may be resumed at the same dose. The same applies if the patient experienced an unacceptable toxicity not specifically described in [Table 6-3](#) or [Section 6.3.3](#), provided this toxicity resolved to  $\leq$  CTCAE grade 1, unless otherwise specified.

### **6.3.2 Permitted study treatment adjustments for Ribociclib**

For patients who are unable to tolerate the protocol-specified dosing schedule, dose reductions or interruptions are permitted to manage drug-related toxicities.

- When dose reduction is necessary, the dose of ribociclib may be reduced to 400 mg.
- If an additional dose reduction is required, ribociclib may be reduced to 200 mg.
- Once the ribociclib dose is reduced it cannot be re-escalated.

- All dose reductions should be based on the worst preceding toxicity.
- Patients are allowed only 2 dose reductions (to 400 mg and 200 mg) as specified in (Table 6-2).

**Table 6-2 Ribociclib dose modifications**

LEE011 Dose Level	LEE011 Dose	Frequency
Starting dose level (0)	600 mg po	Daily (3 weeks on/1 week off)
Dose level – 1	400 mg po	Daily (3 weeks on/1 week off)
Dose level – 2	200 mg po	Daily (3 weeks on/1 week off)

Patients whose treatment is interrupted or permanently discontinued due to an adverse event including abnormal laboratory value must be followed at least once a week for 4 weeks, and subsequently at 4-week intervals, until resolution or stabilization of the event, whichever comes first. The maximum time allowed for treatment interruption due to toxicity is 21 days (3 weeks) from the intended dosing day. If interruption is > 21 days, the patient must be discontinued from the study treatment. However, the patient will continue to be followed for toxicity. Dose interruptions should be reported on the appropriate Dosage Administration eCRF.

### 6.3.3 Criteria for interruption and re-initiation of ribociclib treatment

If the administration of ribociclib must be interrupted because of an unacceptable toxicity, ribociclib dosing will be interrupted or modified according to rules described in Table 6-3.

A patient who requires a dose interruption (regardless of the reason for the interruption) lasting >21 days (counting from the first day when a dose was missed) must discontinue the study treatment.

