**Table 6-4 Recommendations for dose modification in case of hepatic toxicities**

HEPATOTOXICITY (BILIRUBIN, SGPT/ALT, SGOT/AST)	
TOTAL BILIRUBIN without ALT/AST increase above baseline value	
Grade 1 ( $>ULN - 1.5 \times ULN$ ) (confirmed 48-72hrs later)	Maintain dose level with LFTs monitored bi-weekly
Grade 2 ( $> 1.5 - 3.0 \times ULN$ )	Dose interruption of ribociclib If resolved to $\leq$ grade 1 in $\leq 21$ days, then maintain dose level If resolved to $\leq$ grade 1 in $> 21$ days or toxicity recurs, then reduce 1 dose level If toxicity recurs after two dose reductions, discontinue ribociclib
Grade 3 ( $> 3.0 - 10.0 \times ULN$ )	Dose interruption of ribociclib If resolved to $\leq$ grade 1 in $\leq 21$ days, lower 1 dose level of ribociclib If resolved to $\leq$ grade 1 in $> 21$ days or toxicity recurs, discontinue ribociclib

HEPATOTOXICITY (BILIRUBIN, SGPT/ALT, SGOT/AST)	
TOTAL BILIRUBIN without ALT/AST increase above baseline value	
Grade 4 (> 10.0 x ULN)	Discontinue ribociclib
Confounding factors and/or alternative causes for increase of total bilirubin should be excluded before dose interruption/reduction. They include but are not limited to: evidence of obstruction, such as elevated ALP and GGT typical of gall bladder or bile duct disease, hyperbilirubinemia due to the indirect component only (i.e. direct bilirubin component $\leq$ 1 x ULN) due to hemolysis or Gilbert Syndrome, pharmacologic treatment, viral hepatitis, alcoholic or autoimmune hepatitis, other hepatotoxic drugs. For patients with Gilbert Syndrome, these dose modifications apply to changes in direct bilirubin only. Bilirubin will be fractionated if elevated.	
AST or ALT	
AST or ALT without bilirubin elevation > 2 x ULN	
Same grade as baseline or increase from baseline grade 0 to grade 1 (confirmed 48 – 72 hrs later)	No dose adjustment required with LFTs monitored per protocol if same grade as baseline or bi-weekly in case of increase from baseline grade 0 to 1
Increase from baseline grade 0 or 1 to grade 2 (> 3.0 – 5.0 x ULN) or from baseline grade 2 to grade 3 (> 5.0 – 20.0 x ULN)	Dose interruption of ribociclib If resolved to $\leq$ baseline value in $\leq$ 21 days, then maintain dose level If resolved to $\leq$ baseline value in > 21 days or toxicity recurs, then reduce 1 dose level If toxicity recurs after two dose reductions or recovery to $\leq$ baseline value is > 28 days, discontinue ribociclib

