Increase from baseline grade 0 or 1 to grade 3 (> 5.0 – 20.0 x ULN)	Dose interruption of ribociclib until resolved to $\leq$ baseline value, then lower 1 dose level of ribociclib If recovery to $\leq$ baseline value is > 28 days, discontinue ribociclib If toxicity recurs, discontinue ribociclib
Grade 4 (> 20.0 x ULN)	Discontinue ribociclib
AST or ALT and concurrent Bilirubin	
AST or ALT $\geq$ grade 2 (> 3 x ULN) in patients with normal values at baseline and total bilirubin $>$ 2 x ULN or AST or ALT $\geq$ grade 3 (> 5 x ULN) in patients with grade 1 or 2 at baseline, and total bilirubin $>$ 2 x ULN	Discontinue ribociclib
Confounding factors and/or alternative causes for increased transaminases should be excluded before dose interruption/reduction. They include but are not limited to: concomitant medications, herbal preparations or dietary supplements, infection, hepato-biliary disorder or obstruction, new or progressive liver metastasis, and alcohol intake.	

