#### **7.1.3.2 Criteria for premature patient withdrawal (EOT phase completion)**

Patients **may** voluntarily withdraw from the study or be dropped from it at the discretion of the investigator or by the sponsor at any time.

Premature patient withdrawal refers to the point/time when the patient exits from the study treatment prior to the planned completion of all study treatment administration and/or assessments; at this time, all study drug treatment is discontinued and no further assessments are planned, unless the patient will be followed for progression and/or survival.

Patients may be withdrawn from the study treatment if any of the following occur:

- Adverse Event
- Lost to follow-up
- Non-compliance with study treatment
- Physician decision
- Pregnancy
- Progressive Disease
- Protocol deviation
- Study terminated by sponsor
- Subject/guardian decision
- Death
- In addition to the general withdrawal criteria, the following **study specific criteria** will also require study treatment discontinuation:
  - Adjustments to study treatment that result in discontinuation. Please refer to [Section 6.3](#)
  - Use of prohibited medication. Please refer to [Section 6.4.3](#)
  - Interruption of study treatment for > 21 days, regardless of reason, from the intended day of the next scheduled dose

Patients that transition into the rollover clinical trial will perform end of treatment procedures. However, follow-up for safety, survival and disease progression will not be performed.

[REDACTED]

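### Table 6-4's grade 2 bilirubin row restarts patients, with no time limit, where three protocol sections require discontinuation after an interruption of more than 21 days

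*Protocol*

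**What the plan says.** Three places in the protocol set the general rule.

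- **6.3.2, text under Table 6-2:** "The maximum time allowed for treatment interruption due to toxicity is 21 days (3 weeks) from the intended dosing day". It continues: "If interruption is > 21 days, the patient must be discontinued from the study treatment".
- **6.3.3:** a patient whose interruption lasts more than 21 days, whatever its cause, "counting from the first day when a dose was missed) must discontinue the study treatment".
- **7.1.3.2:** the criteria that require treatment to stop include "Interruption of study treatment for > 21 days, regardless of reason, from the intended day of the next scheduled dose".

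Table 6-4 gives the hepatic instructions.

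- **Bilirubin grade 2, resolution after more than 21 days:** "days or toxicity recurs, then reduce 1 dose level If toxicity recurs after two dose reductions, discontinue ribociclib". The only stop is recurrence after two reductions; no number of days ends treatment.
- **Bilirubin grade 3, resolution after more than 21 days:** discontinue.
- **AST/ALT from grade 0 or 1 to grade 2, or from 2 to 3:** "baseline value in > 21 days or toxicity recurs, then reduce 1 dose level". Discontinuation follows only when recovery takes more than 28 days.
- **AST/ALT from grade 0 or 1 to grade 3:** interrupt until recovery, then go one level lower. The row's only time limit is "baseline value is > 28 days, discontinue ribociclib".

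**The concern.** For one patient with slow-resolving grade 2 bilirubin, the general rule says stop and the table says restart one level lower. Both instructions fall within 6.3.3, and nothing says which prevails. Section 6.3.1 comes nearest: "Any planned variance from these guidelines in the view of the patient safety must be previously discussed with the sponsor". That asks for a conversation about planned departures; it does not rank two conflicting protocol rules.

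Hepatic toxicity is one of the major potential toxicities named in protocol section 1.2.1.1.3. At stake is whether sites handle a slow hepatic recovery in the same way. A site that follows either instruction departs from the other.

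**Working it through.** The plan states no figure to reproduce. The check sets the rules side by side and finds the recovery day from which they cannot both be followed.

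**Inputs.** The cap is 21 days (6.3.2, 6.3.3, 7.1.3.2). A cycle is 28 days, 21 on and 7 off (6.1.1). Later cycles are counted from cycle 1 day 1 (7.1.2), so days 1–21 are dosing days, days 22–28 are off and dosing resumes on day 29. Let *d* be the cycle day on which the toxicity is found and *r* the days to recovery. The protocol does not say whether off-week days count toward the 21, so both counts are tried.

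**Missed doses only, *d* a dosing day, that day's dose withheld.** The count is the number of dosing days from *d* to *d + r − 1*.

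- *r* = 28: any 28 consecutive days hold exactly 21 dosing days, so 21 doses are missed. The cap is not exceeded.
- *r* = 29: the 29th day is cycle day *d* again, a dosing day, so 22 doses are missed. The cap is exceeded.

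**Calendar days, same patient.**

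- Restart on the recovery day: length = (*d + r*) − *d* = *r*, which first exceeds 21 at *r* = 22.
- Restart on the next dosing day: if recovery falls on days 22–28, dosing waits until day 29 and the length is 29 − *d*. For *d* = 1, *r* = 21 lands on day 22, giving 29 − 1 = 28 days. For *d* = 7, *r* = 15 also lands on day 22, giving 29 − 7 = 22 days. For *d* = 8 the wait gives 29 − 8 = 21, which does not exceed the cap.

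The conflict therefore starts by day 22 or sooner. Where it starts sooner, it is the row's other branch (resolved within 21 days, keep the dose) that meets the cap.

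**Latest case.** Suppose the toxicity is found on day 21 after that day's dose was taken. The first missed dose is day 29. Days 29–49 hold 21 doses and days 50–56 are off, so the 22nd missed dose is day 57. The cap is exceeded once 21 + *r* ≥ 58, that is *r* ≥ 37. On calendar days the same patient exceeds it once 21 + *r* − 29 > 21, that is *r* ≥ 30. The next latest case is detection on day 22, in the off week: 22 + *r* ≥ 58, so *r* ≥ 36. From *r* = 37 the grade 2 bilirubin row conflicts on both counts for all detection days.

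**AST/ALT rows, *r* = 22 to 28.** At most 21 doses are missed within 28 days, so there is no conflict on a missed-dose count. On a calendar count, the row that explicitly reduces the dose after more than 21 days does conflict, although a toxicity found in the off week starts the interruption clock later and narrows this. The grade 0/1 to 3 row never mentions 21 days; its 28-day stop only implies that a restart on days 22–28 is allowed.

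**The case against.** **The rules can be followed together.** Table 6-4 is titled as recommendations, the cap uses mandatory wording, and rows in Tables 6-3 and 6-6 also hold until recovery without a limit and rely on the cap. This stands in part: a careful site can take the safer 21-day reading. It does not rescue the grade 2 bilirubin row, which names the interval beyond 21 days and directs a restart there.

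**Missed doses are the more coherent count.** Under it 28 days equals 21 doses and the AST/ALT limits fit the cap. SAP 3.5.1.5 also leaves the off week out of its definition of an interruption. On a calendar count, a day 1 hold resolving at 21 days would breach the cap merely by waiting for day 29. Against this, 6.3.2 equates 21 days with 3 weeks and 6.3.3 counts from the first missed day, which favours calendar days. The documents do not settle it, so the AST/ALT point stays conditional. On missed doses, the bilirubin row too is compatible with the cap for recoveries of 22–28 days.

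**Stronger readings a reader might infer.** One is that planned reporting would hide which rule was used, because SAP 3.5.1.5 does not count interruptions that never resume. That is largely answered elsewhere: reasons for discontinuation (SAP 3.3), AE tables for discontinuation and for dose adjustment or interruption (5.1.4), action taken (5.1.3), reportable deviations (3.2) and listings of all data (2.2). Another is that the conflict biases the clinical benefit rate. The documents give no frequency of slow hepatic recovery, so no such effect can be sized.

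**Conclusion.** The grade 2 bilirubin row is wrong as written: it directs a restart, without limit, where three sections require a stop. With detection on a dosing day and that dose withheld, the conflict starts at recovery day 29 on a missed-dose count and by day 22 or sooner on a calendar count. From day 37 it holds on both counts for every detection day. These figures assume the fixed 28-day grid of 7.1.2. They describe the schedule and say nothing about how often recovery takes that long.

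The AST/ALT row for 0/1 to grade 2, or 2 to grade 3, conflicts only if calendar days are meant. The 0/1 to grade 3 row can be followed under either limit. It would be wrong to infer that Table 6-4 as a whole contradicts the cap: the grade 3 bilirubin row agrees with it, and the gravest rows (grade 4 bilirubin, grade 4 AST/ALT, and AST/ALT with concurrent bilirubin) discontinue unconditionally.

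Severity is minor. The safer reading is available, and Amendment 3 reports one patient on study in April 2017, so an edit at that point reaches at most that patient.

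**What to change.** Change the grade 2 bilirubin row so that an interruption of more than 21 days leads to discontinuation, matching 6.3.2, 6.3.3, 7.1.3.2 and the grade 3 bilirubin row. The branch for recurrence can stay.

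Add one sentence stating whether planned off-week days count toward the 21 days, and whether the interruption ends at recovery or at the next dose taken. If calendar days are meant, bring the AST/ALT 28-day limits, and the branch that reduces the dose after more than 21 days, into line with the cap. If only missed doses count, those rows can stand.

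The cost is one edited table row, one clarifying sentence and, on the calendar reading, two further row edits. The mandatory stopping rule is unchanged, and no new data or patients are needed. A clinical study report listing of hepatic interruptions over 21 days, with the rule applied, is optional.

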**Table 6-3 Ribociclib related toxicity management guidelines**

Toxicity	Grade	Dose Adjustment and Management Recommendations
Thrombocytopenia	Grade 1 ≥75 x 10  /L	No dose adjustment required.
	Grade 2 ≥50 x 10  /L – <75 x 10  /L	Dose interruption until recovery to grade ≤1. Re-initiate ribociclib at the same dose.
	Grade 3 ≥25 x 10  /L - <50 x 10  /L	Dose interruption until recovery to grade ≤1. Re-initiate ribociclib at the same dose level. If toxicity recurs at grade 3: temporary dose interruption until recovery to grade ≤1 and reduce ribociclib to the next lower dose level.
	Grade 4 <25 x 10  /L	Dose interruption until recovery to grade ≤1. Re-initiate ribociclib at the next lower dose level. If toxicity recurs at grade 4: discontinue ribociclib.
Absolute neutrophil count (ANC)	Grade 1 ≥1.5 x 10  /L	No dose adjustment required.
	Grade 2 ≥1.0 - <1.5 x 10  /L	No dose adjustment required.

Toxicity	Grade	Dose Adjustment and Management Recommendations
	Grade 3 $\geq 0.5 - <1.0 \times 10^9/L$	Dose interruption until recovery to $\geq 1.0 \times 10^9/L$ . Re-initiate ribociclib at the same dose level. If toxicity recurs at grade 3: temporary dose interruption until recovery to $\geq 1.0 \times 10^9/L$ . If resolved within $\leq 7$ days, then maintain dose level. If resolved $>7$ days, then reduce ribociclib dose to the next lower dose level.
	Grade 4 $<0.5 \times 10^9/L$	Dose interruption until recovery to $\geq 1.0 \times 10^9/L$ . Re-initiate LEE011 at the next lower dose level. If toxicity recurs at grade 4: temporary dose interruption until recovery to $\geq 1.0 \times 10^9/L$ and reduce LEE011 at the next lower dose level.
Febrile neutropenia	Grade 3 ANC $<1.0 \times 10^9/L$ with [a single temperature of $>38.3$ degrees C (101 degrees F) or a sustained temperature of $\geq 38$ degrees C (100.4 degrees F) for more than one hour]	Dose interruption until improvement of ANC $\geq 1.0 \times 10^9/L$ and no fever. Restart at the next lower dose level. If febrile neutropenia recurs, discontinue ribociclib.
	Grade 4 Life-threatening consequences; urgent intervention indicated	Discontinue ribociclib.
Anemia (Hemoglobin)	Grade 1 $\geq 10.0 - LLN$ g/dL	No dose adjustment required.
	Grade 2 $\geq 8.0 - <10.0$ g/dL	No dose adjustment required.
	Grade 3 $<8.0$ g/dL	Dose interruption until recovery to grade $\leq 2$ . Re-initiate ribociclib at the same dose.
	Grade 4 Life-threatening consequences; urgent intervention indicated	Discontinue ribociclib.

**Table 6-4 Recommendations for dose modification in case of hepatic toxicities**

HEPATOTOXICITY (BILIRUBIN, SGPT/ALT, SGOT/AST)	
TOTAL BILIRUBIN without ALT/AST increase above baseline value	
Grade 1 ( $>ULN - 1.5 \times ULN$ ) (confirmed 48-72hrs later)	Maintain dose level with LFTs monitored bi-weekly
Grade 2 ( $> 1.5 - 3.0 \times ULN$ )	Dose interruption of ribociclib If resolved to $\leq$ grade 1 in $\leq 21$ days, then maintain dose level If resolved to $\leq$ grade 1 in $> 21$ days or toxicity recurs, then reduce 1 dose level If toxicity recurs after two dose reductions, discontinue ribociclib
Grade 3 ( $> 3.0 - 10.0 \times ULN$ )	Dose interruption of ribociclib If resolved to $\leq$ grade 1 in $\leq 21$ days, lower 1 dose level of ribociclib If resolved to $\leq$ grade 1 in $> 21$ days or toxicity recurs, discontinue ribociclib

HEPATOTOXICITY (BILIRUBIN, SGPT/ALT, SGOT/AST)	
TOTAL BILIRUBIN without ALT/AST increase above baseline value	
Grade 4 (> 10.0 x ULN)	Discontinue ribociclib
Confounding factors and/or alternative causes for increase of total bilirubin should be excluded before dose interruption/reduction. They include but are not limited to: evidence of obstruction, such as elevated ALP and GGT typical of gall bladder or bile duct disease, hyperbilirubinemia due to the indirect component only (i.e. direct bilirubin component $\leq$ 1 x ULN) due to hemolysis or Gilbert Syndrome, pharmacologic treatment, viral hepatitis, alcoholic or autoimmune hepatitis, other hepatotoxic drugs. For patients with Gilbert Syndrome, these dose modifications apply to changes in direct bilirubin only. Bilirubin will be fractionated if elevated.	
AST or ALT	
AST or ALT without bilirubin elevation > 2 x ULN	
Same grade as baseline or increase from baseline grade 0 to grade 1 (confirmed 48 – 72 hrs later)	No dose adjustment required with LFTs monitored per protocol if same grade as baseline or bi-weekly in case of increase from baseline grade 0 to 1
Increase from baseline grade 0 or 1 to grade 2 (> 3.0 – 5.0 x ULN) or from baseline grade 2 to grade 3 (> 5.0 – 20.0 x ULN)	Dose interruption of ribociclib If resolved to $\leq$ baseline value in $\leq$ 21 days, then maintain dose level If resolved to $\leq$ baseline value in > 21 days or toxicity recurs, then reduce 1 dose level If toxicity recurs after two dose reductions or recovery to $\leq$ baseline value is > 28 days, discontinue ribociclib
Increase from baseline grade 0 or 1 to grade 3 (> 5.0 – 20.0 x ULN)	Dose interruption of ribociclib until resolved to $\leq$ baseline value, then lower 1 dose level of ribociclib If recovery to $\leq$ baseline value is > 28 days, discontinue ribociclib If toxicity recurs, discontinue ribociclib
Grade 4 (> 20.0 x ULN)	Discontinue ribociclib
AST or ALT and concurrent Bilirubin	
AST or ALT $\geq$ grade 2 (> 3 x ULN) in patients with normal values at baseline and total bilirubin $>$ 2 x ULN or AST or ALT $\geq$ grade 3 (> 5 x ULN) in patients with grade 1 or 2 at baseline, and total bilirubin $>$ 2 x ULN	Discontinue ribociclib
Confounding factors and/or alternative causes for increased transaminases should be excluded before dose interruption/reduction. They include but are not limited to: concomitant medications, herbal preparations or dietary supplements, infection, hepato-biliary disorder or obstruction, new or progressive liver metastasis, and alcohol intake.	

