### 6.3.3.1 Additional follow-up for hepatic toxicities

Hepatic toxicity monitoring includes the following LFTs: albumin, ALT, AST, total bilirubin (fractionated if total bilirubin  $>$  2 x ULN), alkaline phosphatase (fractionated if alkaline phosphatase is grade 2 or higher) and GGT. For patients with Gilbert Syndrome: total and direct bilirubin must be monitored, intensified monitoring applies to changes in direct bilirubin only.

Close observation is recommended in case of AST, ALT, and/or bilirubin increase requiring dose interruption, which involves:

- Repeating liver enzyme and serum bilirubin tests **two or three times weekly**. Frequency of re-testing can decrease to once a week or less if abnormalities stabilize or return to normal values.

- Obtaining a more detailed history of current symptoms.
- Obtaining a more detailed history of prior and/or concurrent diseases.
- Obtaining a history of concomitant drug use (including non-prescription medications, herbal and dietary supplements), alcohol use, recreational drug use, and special diets.
- Ruling out acute viral hepatitis types A, B, C, D, and E; hepatotropic virus infections (CMV, EBV or HSV); autoimmune or alcoholic hepatitis; NASH; hypoxic/ischemic hepatopathy; and biliary tract disease.
- Obtaining a history of exposure to environmental chemical agents.
- Obtaining additional tests to evaluate liver function, as appropriate (e.g., INR, direct bilirubin).
- Considering gastroenterology or hepatology consultations.
- Assessing cardiovascular dysfunction or impaired liver oxygenation, including hypotension or right heart failure as possible etiologies for liver dysfunction.

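### Table 6-4 (hepatic dose rules): with bilirubin above 1.5 to 2 x ULN, a confirmed ALT/AST rise from grade 0 to 1 changes the written action from interrupting ribociclib to continuing it; above 2 x ULN, small ALT/AST rises have no row

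*Protocol*

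**What the plan says.** Table 6-4 (Protocol Section 6.3.3) has three blocks, each with its own entry condition.

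- **Block 1, bilirubin.** It is headed "TOTAL BILIRUBIN without ALT/AST increase above baseline value". Grade 1 (above ULN to 1.5 x ULN) keeps the dose. Grade 2 (above 1.5 to 3.0) requires interruption. Grade 3 (above 3.0 to 10.0) requires interruption, then a lower dose if it resolves within 21 days. Grade 4 (above 10.0) requires discontinuation.
- **Block 2, AST or ALT.** It is headed "AST or ALT without bilirubin elevation" above 2 x ULN. Its first row covers "Same grade as baseline or increase from baseline grade 0 to grade 1", confirmed 48 to 72 hours later. The dose is unchanged, and liver tests follow the protocol schedule "or bi-weekly in case of increase from baseline grade 0 to 1". Larger grade rises lead to interruption, interruption with dose reduction, or discontinuation.
- **Block 3, both raised.** Treatment is discontinued when bilirubin exceeds 2 x ULN and ALT/AST reaches grade 2 or more from a normal baseline, or grade 3 or more "in patients with grade 1 or 2 at baseline, and total bilirubin" above 2 x ULN.

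Two follow-up rules depend on the dose action. Section 6.3.3.1 states: "Close observation is recommended in case of AST, ALT, and/or bilirubin increase requiring dose interruption". That means liver tests two or three times weekly and a listed work-up. Section 6.3.2, below Table 6-2, says that patients whose treatment is interrupted or stopped for an adverse event "must be followed at least once a week for 4 weeks, and subsequently at 4-week intervals". Section 6.3.1 adds a general rule: "All dose modifications, interruptions or discontinuations must be based on the worst preceding toxicity".

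**The concern.** The three entry conditions do not fit together. Block 1 switches off when ALT/AST rises above baseline. Block 2 accepts bilirubin up to 2 x ULN, which takes in the lower part of bilirubin grade 2. Block 3 starts only above 2 x ULN and needs a substantial ALT/AST rise. A patient can therefore leave the row that requires interruption because a second liver test has worsened, and land in a row that continues treatment.

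Section 1.2.1.1.3 names hepatic toxicity among the major potential toxicities of ribociclib. At stake is the default instruction to a site: in one combination it says to keep dosing with two abnormal liver signals and to interrupt with one.

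**Working it through.** The plan gives no figure to reproduce. The check applies each block's written condition to the same patient and lists which rows match.

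**Inputs.** Bilirubin and ALT/AST grade limits are those of Table 6-4. The 2 x ULN limit in blocks 2 and 3 splits bilirubin grade 2 into above 1.5 to 2 and above 2 to 3. Baseline ALT/AST above normal is possible, because inclusion criterion 13 allows values below 2.5 x ULN, or up to 5 x ULN with liver metastases.

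**Matching rows at one bilirubin value per band** (initial action as written):

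| Bilirubin (x ULN) | No ALT/AST increase | Rise 0 to 1 (confirmed) | Rise within grade 1 or 2 | Rise 1 to 2 | Rise 0 to 2 |
|---|---|---|---|---|---|
| 1.3 | Keep dose | Keep dose | Keep dose | Interrupt | Interrupt |
| 1.8 | **Interrupt** | **Keep dose** | **Keep dose** | Interrupt | Interrupt |
| 2.5 | Interrupt | No row | No row | No row | Discontinue |
| 5 | Interrupt, then lower dose | No row | No row | No row | Discontinue |
| 11 | Discontinue | No row | No row | No row | Discontinue |

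**Reversal, bilirubin above 1.5 to 2 x ULN.** At 1.8 x ULN with stable ALT/AST, two rows match: bilirubin grade 2 (interrupt) and block 2 row 1 (keep dose). The worst-toxicity rule in Section 6.3.1 points to the stricter one. After a confirmed rise from grade 0 to 1, block 1 is excluded by its heading and block 3 is not reached, because bilirubin is not above 2 x ULN. Only block 2 row 1 remains. It calls for no interruption, so it triggers neither close observation under Section 6.3.3.1 nor the weekly follow-up in Section 6.3.2.

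Block 1's heading refers to baseline value, not grade. Read literally, a rise within grade 1 or 2 has the same effect, and block 2 row 1 then asks only for liver tests on the protocol schedule.

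**Gap, bilirubin above 2 x ULN.** Block 1 is excluded by the ALT/AST rise, block 2 by the bilirubin level, and block 3 by the small size of the ALT/AST rise. This holds even above 10 x ULN, because the grade 4 discontinuation row sits under the same heading.

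**Illustrative count, by grade only.** There are 4 + 3 + 2 = 9 rises from baseline grade 0, 1 or 2 to a higher grade, and five bilirubin bands, so 9 x 5 = 45 combinations. The reversal is 1 of 9 in the band above 1.5 to 2. The gap is 2 of 9 in each of three bands, so 6 of 27. These are table cells, not patients. Because the heading turns on value, a count by grade leaves out the within-grade rises.

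**The case against.** The strongest reply is that block 2 row 1 answers only the ALT/AST question. The concurrent grade 2 bilirubin is then merely unaddressed, and a site would fall back on the worst-toxicity rule or on Table 6-6, whose grade 2 row also says interrupt. Read strictly, block 1's heading would let a trivial ALT rise inside the normal range switch off every bilirubin row, including discontinuation, so a sensible investigator would take it to mean bilirubin as the main abnormality. The table is titled as recommendations, Section 6.3.1 allows a safety variance after discussion with the sponsor or at once if urgent, and Section 7.2.2.5 allows extra laboratory tests.

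Much of this stands as a prediction of practice. It does not repair the text. Block 2's heading expressly admits patients with bilirubin up to 2 x ULN, so in that band a row does match and does give an action. The worst-toxicity rule supplies no hepatic action of its own, and the row it would point to is excluded by its own heading. Table 6-6 is for all other adverse reactions. A safe default should not depend on a variance.

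Three stronger readings are tempting, and the documents do not support them:

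- **That liver testing falls by a set number of tests.** Bi-weekly can mean every two weeks or twice a week, row 1 adds a confirmatory test at 48 to 72 hours, and close observation is only recommended and can be relaxed once values stabilize. No test count should be claimed.
- **That patients above 2 x ULN get a weaker action.** They have no row. The likely fallbacks (block 1 rows, Table 6-6, the worst-toxicity rule) lead to the same initial action as bilirubin alone.
- **That block 3's higher threshold for patients with raised baseline ALT/AST is a mistake.** The table sets it out separately, and it reads as deliberate.

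**Conclusion.** The point holds as a low-severity correction to a safety rule. In one bilirubin band, above 1.5 to 2 x ULN, a confirmed ALT/AST rise from grade 0 to 1 turns a written interruption into written continuation. Within-grade rises do the same if the heading is read literally. Above 2 x ULN the table is silent for small rises, which is a gap and no more.

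The conclusion assumes that the block headings are entry conditions and that row 1's confirmation has been obtained. Until it has, row 1 is not met either, so the reversal is not established at first detection.

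A reader might infer meaningful exposure of trial patients. The documents do not support that. They give no rate of combined elevation. Enrollment closed on May 8, 2015, one patient remained on study as of April 6, 2017, and Amendment 3's main purpose is to let that patient move to a rollover study. No efficacy endpoint or statistical figure is affected.

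**What to change.** Make two wording changes to Table 6-4:

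1. Replace the block 1 condition, for example with: *Total bilirubin, when the criteria for concurrent AST/ALT and bilirubin elevation are not met, whatever the ALT/AST change.*
2. Add one line: *When a bilirubin row and an ALT/AST row both apply, the stricter action governs.*

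No other row is needed. At 1.8 x ULN with a rise of 0 to 1, the grade 2 bilirubin row now applies from first detection and gives interruption, with its follow-up. At 2.5, 5 and 11 x ULN, rises of 0 to 1, 1 to 2 or within a grade take the bilirubin row: interrupt; interrupt then lower dose; discontinue. On the illustrative count by grade, 1 of 45 combinations becomes stricter, 6 gain a row, and 45 - 1 - 6 = 38 keep their action.

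The cost is a wording amendment with the ethics approval that Section 12.1 requires, and a memo to sites. The clinical downside is a few more interruptions with closer liver-test follow-up, in this trial at most in the one remaining patient. If that patient has already moved to the rollover study, the change reaches no one here.
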